## 7.3 Concomitant Medications, Treatments, and Procedures

Not Applicable

## 7.4 Justification for Sensitive Procedures

There are no sensitive procedures, provocative testing or deception inherent in this study.

## 7.5 Prohibited Medications, Treatments, and Procedures

Not applicable

## 7.6 Prophylactic Medications, Treatments, and Procedures

Not applicable

## 7.7 Rescue Medications, Treatments, and Procedures

Not applicable

## 7.8 Participant Access to Study Agent at Study Closure

Not applicable. Should the individual still be receiving HHC from the intervention team at the close of the study period they will continue to receive the intervention.

## 8 Assessment of Safety

- 8.1 This study is a minimal risk study given that it is an evidence-based implementation science intervention. However, the investigators will monitor for the following safety parameters and events throughout this study. In instances where an adverse event (AE) or a serious adverse event (SAE) has been identified, the investigators will follow standard clinical practice (SCP) whereby the investigator will notify the subject's health care provider responsible for initiating and/or approving the subject's enrollment into HHC services. In situations where an AE or SAE has been determined to be related to the study and the subject has withdrawn, investigators will actively monitor in follow up. Specification of Safety Parameters

CONFIDENTIAL

This material is the property of the NYU School of Medicine and Langone Medical Center. Do not disclose or use except as authorized in writing by the study sponsor  
 Interventional Template Version: 28 APR 2017

Due to the pragmatic nature of the trial, the DSMB has directed this trial to perform a highly focused AE collection process which requires following single adverse event: a PHQ-9 score worsened by greater than or equal to 5 points during the course of the study. The DSMB further requires monitoring the following severe AEs: Caregiver attempted suicide; death of caregiver; death of person with dementia a; medical event that may jeopardize the subject, including hospitalization of either the person with dementia or caregiver, suicidal ideation, elder neglect or abuse, or an environmental threat such as unsecured firearm.

In cases of the following safety parameters, the site-PI and PI shall be notified immediately, a telephone triage performed, and then SCP will be followed by notifying the subject's primary care provider to advise of the situation.

Due to the virtual nature of data collection, safety monitoring will be done to the best of abilities for:

- Imminent home safety threats/hazards (e.g. hoarding/cluttering, unsecured gun).**
- Suspected elder abuse or neglect.**

**Caregiver Depression:** Should caregivers have a score of  $\geq 10$  on the PHQ-9 or exhibit suicidal ideation via item 9 of the PHQ-9 or verbally outside of any instrumentation, Definition of Adverse Events (AE)

**An adverse event (AE)** is any symptom, sign, illness or experience that develops or worsens in severity during the course of the study. Intercurrent illnesses or injuries should be regarded as adverse events. Abnormal results of diagnostic procedures are considered to be adverse events if the abnormality:

- results in study withdrawal
- is associated with a serious adverse event
- is associated with clinical signs or symptoms
- leads to additional treatment or to further diagnostic tests
- is considered by the investigator to be of clinical significance

The following AEs will be monitored in this study:

Worsening of depression symptoms: Caregivers whose PHQ-9 score worsen by greater than or equal to 5 points during the course of the study

### 8.1.1 Definition of Serious Adverse Events (SAE)

#### **Serious Adverse Event**

Adverse events are classified as serious or non-serious. A **serious adverse event** is any AE that is:

- fatal
- life-threatening
- requires or prolongs hospital stay
- results in persistent or significant disability or incapacity
- a congenital anomaly or birth defect
- an important medical event

Important medical events are those that may not be immediately life threatening but are clearly of major clinical significance. They may jeopardize the subject and may require intervention to prevent one of the other serious outcomes noted above. For example, drug overdose or abuse, a seizure that did not result in in-patient hospitalization, or intensive treatment of bronchospasm in an emergency department would typically be considered serious.

All adverse events that do not meet any of the criteria for serious should be regarded as **non-serious adverse events**.

The following SAEs will be monitored in this study:

**CONFIDENTIAL**

This material is the property of the NYU School of Medicine and Langone Medical Center. Do not disclose or use except as  
authorized in writing by the study sponsor

Caregiver attempted suicide: A case in which a caregiver is noted to have attempted suicide. This information may be provided by the PWD surrogate, PWD (if only mild dementia) or other family member, friend, or caregiver when attempting to complete follow-up visits.

Death of Caregiver: A case in which a caregiver is noted to have died. This information may be provided by the PWD surrogate, PWD (if only mild dementia) or other family member, friend, or caregiver when attempting to complete follow-up visits. We will attempt to ascertain the cause of death of the caregiver

Death of PWD: A case in which the PWD has died. We will attempt to contact the caregiver and primary care provider to ascertain the cause of death.

Any SAE will be immediately reported to the site-PI and overall PI, who will follow SCP by notifying the subject's health care provider and then notifying the IRB of record and DSMB for further review.

### 8.1.2 **Definition of Unanticipated Problems (UP)**

#### **Unanticipated Problems Involving Risk to Subjects or Others**

Any incident, experience, or outcome that meets all of the following criteria:

- Unexpected in nature, severity, or frequency (i.e. not described in study-related documents such as the IRB-approved protocol or consent form, the investigators brochure, etc)
- Related or possibly related to participation in the research (i.e. possibly related means there is a reasonable possibility that the incident experience, or outcome may have been caused by the procedures involved in the research)
- Suggests that the research places subjects or others at greater risk of harm (including physical, psychological, economic, or social harm).

This definition could include an unanticipated serious adverse effect on health or safety or any life-threatening problem or death caused by, or associated with, the intervention, if that effect, problem, or death was not previously identified in nature, severity, or degree of incidence in the investigational plan or application (including a supplementary plan or application), or any other unanticipated serious problem associated with a device that relates to the rights, safety, or welfare of subjects (21 CFR 812.3(s)).

## 8.2 **Classification of an Adverse Event**

### 8.2.1 **Severity of Event**

For AEs not included in the protocol defined grading system, the following guidelines will be used to describe severity.

- **Mild** – Events require minimal or no treatment and do not interfere with the participant's daily activities.
- **Moderate** – Events result in a low level of inconvenience or concern with the therapeutic measures. Moderate events may cause some interference with functioning.
- **Severe** – Events interrupt a participant's usual daily activity and may require systemic drug therapy or other treatment. Severe events are usually potentially life-threatening or incapacitating.

### 8.2.2 **Relationship to Study Quality Improvement Program**

CONFIDENTIAL

This material is the property of the NYU School of Medicine and Langone Medical Center. Do not disclose or use except as authorized in writing by the study sponsor  
 Interventional Template Version: 28 APR 2017

The PI or site PI will assess the AE's relationship to study quality improvement program, and will be part of the documentation process, but it is not a factor in determining what is or is not reported in the study. If there is any doubt as to whether a clinical observation is an AE, the event should be reported. All AEs must have their relationship to study agent assessed. In a clinical trial, the study product must always be suspect. To help assess, the following guidelines are used.

- **Related** – The AE is known to occur with the study agent, there is a reasonable possibility that the study agent caused the AE, or there is a temporal relationship between the study agent and event. Reasonable possibility means that there is evidence to suggest a causal relationship between the study agent and the AE.
- **Not Related** – There is not a reasonable possibility that the administration of the study agent caused the event, there is no temporal relationship between the study agent and event onset, or an alternate etiology has been established.

### 8.2.3 Expectedness

The site PI or PI will be responsible for determining whether an AE is expected or unexpected. An AE will be considered unexpected if the nature, severity, or frequency of the event is not consistent with the risk information previously described for the study agent.

## 8.3 Time Period and Frequency for Event Assessment and Follow-Up

The occurrence of an AE or SAE may come to the attention of study personnel during study visits and interviews of a study participant presenting for medical care, or upon review by a study monitor. All AEs including local and systemic reactions not meeting the criteria for SAEs will be captured on the appropriate RF. Information to be collected includes event description, time of onset, clinician's assessment of severity, relationship to study product (assessed only by those with the training and authority to make a diagnosis), and time of resolution/stabilization of the event. All AEs occurring while on study must be documented appropriately regardless of relationship. All AEs will be followed to adequate resolution.

Any medical condition that is present at the time that the participant is screened will be considered as baseline and not reported as an AE. However, if the study participant's condition deteriorates at any time during the study, it will be recorded as an AE. UPs will be recorded in the data collection system throughout the study.

Changes in the severity of an AE will be documented to allow an assessment of the duration of the event at each level of severity to be performed. AEs characterized as intermittent require documentation of onset and duration of each episode.

The PI will record all reportable events with start dates occurring any time after informed consent is obtained until 7 (for non-serious AEs) or 30 days (for SAEs) after the last day of study participation. At each study visit, the investigator will inquire about the occurrence of AE/SAEs since the last visit. Events will be followed for outcome information until resolution or stabilization.

All unresolved adverse events should be followed by the investigator until the events are resolved, the subject is lost to follow-up, or the adverse event is otherwise explained. At the last scheduled visit, the investigator should instruct each subject to report any subsequent event(s) that the subject, or the subject's personal physician, believes might reasonably be related to participation in this study. The investigator should notify the study sponsor of any death or adverse event occurring at any time after a subject has discontinued or terminated study participation that may reasonably be related to this study. The sponsor should also be notified if the investigator should become aware of the development of cancer or of a congenital anomaly in a subsequently conceived offspring of a subject that has participated in this study.

CONFIDENTIAL

This material is the property of the NYU School of Medicine and Langone Medical Center. Do not disclose or use except as authorized in writing by the study sponsor

## **8.4 Reporting Procedures – Notifying the IRB**

All AEs and SAEs will be reported to the site-PI (if applicable) and study-PI immediately. The PI will assess the event for severity, consult with the co-investigators if necessary, and when an event has been determined to be severe, the site PI will follow SCP by notifying the subject's health care provider. The PI will report all study related SAEs to IRB and DSMB within 24 hours of their knowledge of the incident. The PI will be responsible for working with the DSMB, IRB, site-PIs and other individuals regarding related SAE to the trial. All AEs will be recorded and reviewed immediately and for patterns of AE on a quarterly basis and referred with a corresponding report to the IRB and DSMB.

### **8.4.1 Unanticipated Problem Reporting**

Incidents or events that meet the OHRP criteria for UPs require the creation and completion of an UP report form. It is the site investigator's responsibility to report UPs to their IRB and to the DSMB/study sponsor. The UP report will include the following information:

- Protocol identifying information: protocol title and number, PI's name, and the IRB project number;
- A detailed description of the event, incident, experience, or outcome;
- An explanation of the basis for determining that the event, incident, experience, or outcome represents an UP;
- A description of any changes to the protocol or other corrective actions that have been taken or are proposed in response to the UP.

To satisfy the requirement for prompt reporting, UPs will be reported using the following timeline:

- UPs that are SAEs will be reported to the IRB and to the DSMB/study sponsor within 24 hours of the investigator becoming aware of the event.
- Any other UP will be reported to the IRB and to the DSMB/study sponsor within 3 days of the investigator becoming aware of the problem.
- All UPs should be reported to appropriate institutional officials (as required by an institution's written reporting procedures), the supporting agency head (or designee), and OHRP within<insert timeline in accordance with policy> of the IR's receipt of the report of the problem from the investigator.

## **8.5 Reporting Procedures – Notifying the Study Sponsor**

The study clinician will complete a SAE Form within the following timelines:

- All deaths and immediately life-threatening events, whether related or unrelated, will be recorded on the SAE Form. SAE that have been determined to be related to the study will be submitted to the DSMB/study sponsor within 24 hours of site awareness. See Section 1, Key Roles for contact information.
- Other SAEs that are determined to be related to the study will be submitted to the DSMB/study sponsor within 72 hours of site awareness.

All SAEs will be followed until satisfactory resolution or until the site investigator deems the event to be chronic or the adherence to be stable. Other supporting documentation of the event may be requested by the DSMB/study sponsor and should be provided as soon as possible.

As a follow-up to the initial report, within the following 48 hours of awareness of the event, the investigator shall provide further information, as applicable, on the unanticipated event or the unanticipated problem in the form of a written narrative. This should include a copy of the completed Unanticipated Problem form,

CONFIDENTIAL

This material is the property of the NYU School of Medicine and Langone Medical Center. Do not disclose or use except as authorized in writing by the study sponsor

and any other diagnostic information that will assist the understanding of the event. Significant new information on ongoing unanticipated adverse effects shall be provided promptly to the study sponsor.

## **8.6 Reporting Procedures – Participating Investigators**

As noted in 8.4 all site PIs will take part in the classification of AEs, SAEs and UPs and will therefore be immediately contacted for discussion of the event.

## **8.7 Study Halting Rules**

Temporary suspension of the trial will occur if there is a 20% or greater negative effect found in any of the primary outcomes. The study will also be halted if SAEs are found that are caused by the quality improvement program, or at the discretion of the IC or the DSMB in conjunction with the IC. Safety Oversight

It is the responsibility of the Principal Investigator to oversee the safety of the study at his/her site. This safety monitoring will include careful assessment and appropriate reporting of adverse events as noted above, as well as the construction and implementation of a site data and safety-monitoring plan. Medical monitoring will include a regular assessment of the number and type of serious adverse events.

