## Protocol Summary

Title	A Multisite cluster RCT of the dementia symptom management at home program
Brief Summary	Alzheimer's Disease and Related Disorders (dementia) poses a significant challenge to our public health. While many persons with dementia are cared for by friends and family in the community with the assistance of home healthcare, most home healthcare clinicians and agencies are ill prepared to care for this population and therefore have difficulty assisting patients and caregivers in maintaining quality of life leading to adverse patient outcomes, increased caregiver stress and burnout, and healthcare utilization. This study will therefore utilize a cluster randomized controlled design at 3 study sites to examine the ability of a multi-component evidence-based practice primary palliative care quality improvement program for home healthcare registered nurses, occupational therapists and physical therapists to improve the quality of life and reduce healthcare utilization for persons with dementia and their informal caregiver.
Phase	3
Objectives	
1) Measure the effects of the DSM-H on quality of life (primary) and pain and BPSD severity (secondary) in the PWD.
 
2) Assess the effects of the DSM-H on quality of life (primary), and physical and mental health (secondary) in the informal caregiver of the PWD.
 
3) Assess the effects of the DSM-H on healthcare utilization in the PWD. Primary outcomes are ER visits and hospital admission rates. Secondary outcomes are outpatient visits and primary care provider contacts.

Methodology	Multi-site cluster randomized controlled trial of a quality improvement program
Endpoint	
Primary Endpoints: PWD and caregiver QOL. Number of PWD ER visits and inpatient admissions
 
Secondary Endpoints: PWD Pain and severity of individual BPSD, antipsychotic and analgesic use. PWD outpatient visits and primary care provider contacts. Caregiver burden, depression, functional health and well-being.

Study Duration	3.75 years
Participant Duration	60 days

CONFIDENTIAL

This material is the property of the NYU School of Medicine and Langone Medical Center. Do not disclose or use except as authorized in writing by the study sponsor

Interventional Template Version: 28 APR 2017

[figure not shown]

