***Aim 3: Assess the effects of the DSM-H on healthcare utilization in the PWD.***

H3: PWD cared for by a HHC team utilizing the DSM-H performance improvement program will show a reduction in emergency room visits and hospital admissions compared to the control (usual care) group, and a greater number of outpatient visits.

The primary outcomes to be measured are the number of emergency room visits and hospital admission rates of the PWD at 30 and 60 days. It will be measured through interviews with the informal caregiver using the Resource Utilization Inventory.

CONFIDENTIAL

This material is the property of the NYU School of Medicine and Langone Medical Center. Do not disclose or use except as authorized in writing by the study sponsor  
 Interventional Template Version: 28 APR 2017

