### **5.8 Premature Termination or Suspension of Study**

This study may be temporarily suspended or prematurely terminated if there is sufficient reasonable cause. Written notification, documenting the reason for study suspension or termination, will be provided by the suspending or terminating party to the principle investigator, the NIA program officer, and the DSMB. If the study is prematurely terminated or suspended, the PI will promptly inform the IRB and will provide the reason(s) for the termination or suspension.

Circumstances that may warrant termination or suspension include, but are not limited to:

- Determination of unexpected, significant, or unacceptable risk to participants

CONFIDENTIAL

This material is the property of the NYU School of Medicine and Langone Medical Center. Do not disclose or use except as authorized in writing by the study sponsor

- Insufficient compliance to protocol requirements
- Data that are not sufficiently complete and/or evaluable
- Determination of futility
- DSMB or NIH halts study for any other reasons not listed above.

Study may resume once concerns about safety, protocol compliance, data quality are addressed and satisfy the NIH, IRB and DSMB.

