## **8.8 Safety Oversight**

### **8.8.1 Data Safety and Monitoring**

The Principle Investigator will ensure overall safety of the subjects in the trial on a daily basis and will be responsible for all reporting. The site PIs will be responsible for managing safety at their sites in coordination with the PI. The study statistician will be responsible for running quarterly reports on data safety, consistency and outcomes and reviewing them with the study PI. A DSMB will act in an advisory capacity to the Primary IC Director in regards to the study.

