### **8.8.2 Frequency and Reporting**

As noted in [section 8.4](#), all AE and SAE will be reported directly to the site PI and then study PI. All events will be reported within 24 hours to the DSMB and the IRB at both the study site and the primary IRB (NYU). The DSMB will then discuss whether and how to convene. Outside of SAE, the DSMB will meet at least prior to onset of the trial and every 6 months at a minimum. Safety reports will be sent twice yearly including analysis of study progress and data and safety issues. These reports will include descriptive analyses of participant demographic data, interim analyses of primary and secondary outcomes, as well as any adverse or serious adverse events, and quality improvement program fidelity. Individuals who withdraw from the trial will be examined in sensitivity analyses, however will be replaced with completed cases for the purposes of the trial. There are no cases where the quality improvement program will be discontinued but follow-up will still occur unless an individual withdraws from the study due to an AE or SAE, in which case we will ensure safety of the individual/dyad and referral to existing resources.

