## 10.4 Description of Statistical Methods

### 10.4.1 General Approach

Data Analysis will be performed using SAS 9.4. We will perform statistical tests to examine baseline differences between the quality improvement program and control groups. We will then perform unadjusted comparison of both primary outcomes (patient and caregiver quality of life, emergency room visits) and secondary outcomes (pain, BPSD, delirium, caregiver depression burden, and burnout, hospital and emergency room admissions) between groups. We will focus on the endpoint measure for quality of life, and 30 and 60-day outcomes for emergency room utilization. For primary and secondary outcomes, we will perform a time trend analysis using a mixed effects linear model (PROC MCM). Mixed effects regression is used to analyze longitudinal data with repeated measures accounting for intra-individual and group clustering. We intend to use multivariate mixed effects regression modeling as opposed to traditional linear modeling or ANOVA in order to control for unobservable confounding variables that are constant over time but differ across PWD and/or caregivers. For both primary and secondary outcomes, we will then repeat the above analyses adjusting for baseline variables as covariates for a more efficient measurement of the effects of the quality improvement program. We will also perform correlation analyses to explore the relationship between pain and BPSD, and PWD and caregiver QOL through plotting scores over time and then if a significant correlation is present through adding to our mixed effect model. For utilization data, we will perform logistic regression to examine whether the patient is more or less likely to have a hospitalization or ER visit compared when receiving the quality improvement program at 30 and 60 days. We will then perform a Poisson Count Regression to compare the total number of hospitalizations and ER visits at each timepoint. In these models we will utilize a random effect to measure for clustering.

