### 10.4.2 Safety Analyses

We will perform interim analyses using descriptive statistics and two-sided t-tests, monitoring for a significance of 0.05 starting at the end of year 1 of the grant for safety purposes. These results will be presented unblinded to the DSMB.

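### The interim harm tests in 10.4.2 ignore care-team clustering; the 20% trigger in 8.7 has no precision or minimum-data condition; and 8.8.3.1.2 and 10.4.5.2 disagree on halting for benefit

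*Combined protocol and SAP*

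**What the plan says.** **Interim tests.** Section 10.4.2: "We will perform interim analyses using descriptive statistics and two-sided t-tests, monitoring for a significance of 0.05 starting at the end of year 1". Results go unblinded to the DSMB. The section names neither the unit of analysis nor a cluster term. Section 10.5, by contrast, treats control of intra-class correlation as obligatory and powers the trial at ICC .05. Section 10.4.1 plans mixed models that account for group clustering, and a random effect in the utilization models.

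**Suspension trigger.** Section 8.7: "Temporary suspension of the trial will occur if there is a 20% or greater negative effect found in any of the primary outcomes". Section 10.4.5.1 cites 8.7 and 10.4.2 together but does not say whether significance is also needed. Section 5.8 allows a restart: "Study may resume once concerns about safety, protocol compliance, data quality are addressed and satisfy the NIH, IRB and DSMB".

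**Looks.** Section 8.8.2: "Safety reports will be sent twice yearly". Section 8.8.1 also has the statistician "running quarterly reports on data safety, consistency and outcomes and reviewing them with the study PI".

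**Which outcomes are primary.** The Protocol Summary gives "Number of PWD ER visits and inpatient admissions", and Aim 3 says "The primary outcomes to be measured are the number of emergency room visits and hospital admission rates of the PWD"; 4.2.1 agrees. Section 10.4.1 gives "primary outcomes (patient and caregiver quality of life, emergency room visits" and puts hospital admissions on the secondary list, where emergency room use appears again.

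**Halting for benefit.** Section 8.8.3.1.2 lets the DSMB recommend halting when outcomes are significantly better. Section 10.4.5.2 rules efficacy out of any halting decision, without qualification.

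**The concern.** The trial randomizes 20 care teams, not dyads. An ordinary t-test on dyads treats patients of one team as independent, so its standard error is too small, and increasingly so as teams fill up. The DSMB would see p-values that overstate the evidence, most of all late in the trial.

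The 20% clause has the opposite weakness. It attends to the estimate and not to its uncertainty, so with few dyads chance alone can cross it. For a score such as QOL-AD it may be so wide that it does not notice a harm the protocol calls meaningful. At stake is an unwarranted or a missed pause. The suspension is temporary, so the loss of the trial is not the issue.

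The two statements on halting for benefit leave the DSMB without a clear mandate if interim results look favourable.

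**Working it through.** **1. The plan's own figure.** Section 10.5 claims power .80 at δ = .45 with 20 clusters of 15 and ICC .05. Var = 4[.05 + .95/15]/20 = .0227, so SE = .1506 and .45/.1506 = 2.99. With 18 degrees of freedom the power is .807. The claim reproduces, and only with clustering included. The interim tests leave out what this calculation relies on.

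**2. Look timing (inferred).** Enrolment starts in month 6 at 9 dyads per month (5.4). Add a 60-day lag, 15% loss (10.5), a first look at month 12 (10.4.2) and six-monthly looks (8.8.2). At month 12: 9 × (12 − 7) × .85/20 = 1.9 completers per team. Later looks give 4.2, 6.5, 8.8, 11.1, 13.4 and then the target of 15. Enrolment closes in month 45, so month 42 is the last look while it is open.

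**3. True error of the ordinary t-test.** DE = 1 + (m − 1) × .05; error = 2 × [1 − Φ(1.96/√DE)]. The last column comes from 40,000 simulated trials with 10 teams per arm and one continuous outcome.

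| Month | m per team | DE | Formula | Simulated |
|---|---|---|---|---|
| 12 | 2 | 1.05 | 5.6% | 5.6% |
| 18 | 4 | 1.15 | 6.8% | 6.9% |
| 24 | 7 | 1.30 | 8.6% | 8.7% |
| 30 | 9 | 1.40 | 9.8% | 10.1% |
| 36 | 11 | 1.50 | 11.0% | 11.1% |
| 42 | 13 | 1.60 | 12.1% | 12.1% |
| 48 | 15 | 1.70 | 13.3% | 13.4% |

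The chance of significance at some look is about 23% over six looks and 25% over seven. With no clustering, repetition alone gives about 17%. A t-test on care-team means (18 df) stays at 4.9–5.2% at every look. At 15 per team the ordinary test's error is 6.5% if the ICC is .01 and 21% if it is .10.

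**4. The 20% trigger, ER visits.** Section 4.2.1 equates a 10% reduction with 220 fewer ER visits per 1000 patients. Read as a relative change, the base rate is 220/1000/.10 = 2.2 per person.

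- Hand check, first look: 20 per arm × 2.2 = 44 expected visits. SE of the log ratio is √(2/44) = .213; ln 1.2 = .182; .182/.213 = .86. The null chance of crossing is about 20% before clustering or overdispersion.
- Simulation over the looks with ICC .05 gives about 28–49%, from Poisson to overdispersed counts.
- Without the first look it is 19–39%. Counting only looks from 7 per team it is 11–31%. At the final look alone it is 4–17%.
- Clustering adds little to the pooled figure (26 to 29% Poisson, 47 to 49% overdispersed). Small early samples and repetition drive it.

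**5. The 20% trigger, QOL-AD.** Mean 33.1, SD 5.9 (10.5). 20% of the mean is .20 × 33.1 = 6.62 points, and 6.62/5.9 = 1.12 SD. With a true harm of 0.5 SD, the size 4.2.1 calls meaningful, this is crossed in about 3% of trials. Read instead as 0.2 SD, it is crossed in 38–39% of null trials. Caregiver QOL has no mean or SD in the documents, so nothing is computed for it.

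**The case against.** - **Judgement stands between estimate and action.** 8.8.1 makes the DSMB advisory, and 8.8.3.1.2, citing 8.7, ties a halt of the programme to closure by the funding institute or to a DSMB recommendation on safety. This stands. A reader might infer from 8.7 that most null trials would be suspended automatically. The documents do not support that, so the figures above are threshold-crossing rates.
- **The scale is less open for utilization than it could seem.** 4.2.1 states the Aim 3 effect as a percent change in events. An odds ratio or a percentage-point reading is possible, because 10.4.1 plans an odds model too, but it is less natural. No weight is put on those readings here. For the QOL scores the scale does remain open.
- **10.4.5.1 cites both sections, so significance may also be required.** If so, ER crossings fall to 11–12%. The text does not say so.
- **The month-48 look comes after enrolment closes.** True. The figure that matters for pausing recruitment is the 12% at month 42.
- **Ignoring clustering is read from silence.** Also true, but a plain two-sided t-test is ordinarily a dyad-level test, and the plan names the cluster term where it intends one.
- **An over-sensitive harm screen can be a deliberate choice.** Defensible, but the plan does not present it as one, and the excess error grows with the data.
- **Details may sit in the site safety-monitoring plan or the Study Manual**, which are not available here.

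**Conclusion.** The point holds in three parts, as something the sponsor should correct.

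First, and most firmly, the tests named in 10.4.2 contradict the plan's own requirement in 10.5. The distortion is slight at the first look and more than doubles the nominal 5% by the later ones. This rests on ICC .05, even accrual across teams and a dyad-level reading. By symmetry about half of the error falls in the direction of harm. A reader might infer that the trial's type I error is inflated, or that these tests trigger suspension. Neither follows: this is the error of a safety screen, and 8.7 does not refer to the tests.

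Second, 8.7 applied to a bare estimate would often flag a null programme on ER visits and almost never flag a meaningful QOL-AD harm when read as a percent of the mean. The ER range depends on an inferred base rate and on a very small first look. A reader might also take 10.4.1 to make ER visits the only primary utilization outcome. It places emergency room use on both lists, so it settles nothing.

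Third, 8.8.3.1.2 and 10.4.5.2 contradict each other. That the DSMB only recommends does not remove the conflict, since 10.4.5.2 is unqualified.

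**What to change.** 1. **10.4.2:** replace the ordinary t-tests with the cluster-adjusted models already planned in 10.4.1, or with a t-test on care-team means at early looks. Standard errors widen by about 2% at 2 per team (√1.05 = 1.02) and 30% at 15 (√1.70 = 1.30). A test on team means detects a true 0.5 SD harm in about 31% of trials at the first look and 88% at the last, against 34% and 97%; part of that late advantage is bought with the 13% error. The error from repeated looks remains, and the DSMB should be told its size.
2. **8.7:** with the DSMB, base the trigger on an estimate with care-team-adjusted uncertainty, from a stated amount of data and on a stated scale for each outcome. Settle which utilization outcomes are primary and which look applies. Report the rule's false-trigger and detection rates. The threshold stays the DSMB's choice. Any data minimum costs detection: on a bare rate-ratio reading, a true 30% rise in both ER visits and admissions is flagged in 92–97% of trials over seven looks, and in 85–94% if looks below 7 per team do not count.
3. **8.8.3.1.2 and 10.4.5.2:** reconcile them, noting that the open-ended list in 5.8 does not name efficacy.

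The work is protocol and DSMB wording plus a short simulation. No new data or models are needed.
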